whether the patient may be interested in learning more about the study and potentially partaking in the study. If the patient says yes, then the Co-I will go over the consent form with the patient and explain that if the patient chooses to partake in the study, then he/she will randomly receive either the Buzzy® device or the numbing injection. The Co-I will answer any questions that the patient may have. If the patient consents to partaking in the study, then the Co-I will follow the randomization sheet with which pain-relieving technique to be administered to the patient. The Co-I will administer the appropriate technique and place the peripheral intravenous catheter.

Specifics of how the two interventions will be performed:

Experimental group - *Buzzy® device*: Subjects in this group will have the Buzzy® device applied to them. The Buzzy® consists of two components: (1) body of the bee, which provides vibration, and (2) removable and reusable ice wings, which provide the cold sensation. The body of the bee is powered by two alkaline AAA batteries, which could last for approximately 20 hours. There is a manual switch on the top part of the body of the bee that is used to activate and deactivate the vibration. The removable set of ice wings contain a total of 18 grams of ice and can stay frozen for about 10 minutes when exposed to room temperature. The Co-I who will be applying the Buzzy® device will follow the manufacturer's (MMJ Labs, Atlanta, Georgia, USA) recommendations and will (1) retrieve the set of ice wings from the freezer in the Preop Unit immediately before the peripheral intravenous catheter procedure, (2) insert the ice wings through the elastic bands fixed on the back of the Buzzy® device, (3) secure the Buzzy® device on the subject's arm with a reusable tourniquet, about 3-5cm proximal to where the peripheral intravenous catheter will be inserted, (4) turn the manual switch of the device on, (5) clean and prepare the area where the peripheral intravenous catheter will be inserted, (6) insert the peripheral intravenous catheter approximately 60 seconds after the Buzzy® device was applied, (7) keep the device turned on throughout the procedure, until at least the needle is removed, (8) remove the Buzzy® device and clean both components of the device (body of bee and ice wings) with a disinfectant cleaner, (9) and place the ice wings back in the freezer of the unit for a subsequent procedure.

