Control group - *Intradermal lidocaine 2%*: Subjects in this group will have the intradermal lidocaine 2% administered to them. An individual vial of Lidocaine 2% will be utilized per subject. The lidocaine will be drawn up into a 3cc syringe, using a 25G needle. The Co-I will apply a reusable tourniquet to the subject's arm about 3-5cm proximal to where the peripheral intravenous catheter will be inserted. The area where the peripheral intravenous catheter will be inserted will be cleaned with an alcohol wipe. Lidocaine will then be injected intradermally, forming a small wheel underneath the skin. Within about 60 seconds of the intradermal injection, the peripheral intravenous catheter will be inserted. The remains of the lidocaine, lidocaine vial, needle, and syringe will be properly disposed into the sharps container.

The Co-I will fill out the top part of the questionnaire that is found below and ask the subject to fill out the bottom half of the questionnaire. The subject will then place the questionnaire into an envelope, without revealing the answers to the Co-I. This way the subject may feel more comfortable answering the questionnaire truthfully.

Once all subjects are enrolled, the data from the questionnaires will be entered into an excel sheet by one of the Co-I's. Data entry will be re-checked by another research team member to assure accuracy of data entry. Once data entry is complete, one of the Co-I's will perform the statistical analysis and the statistical analysis will be re-checked by a second research team member.

[Please note that we are aware that because of the current COVID-19 pandemic, most non-COVID-19 related studies are being placed on hold to minimize unnecessary interactions with patients. However, we would appreciate consideration of this study being done now since all the people that will be obtaining consent and conducting the study will be the essential personnel that will either way (regardless of whether the study will be taking place) will be taking care of these patients and placing those peripheral intravenous catheters. We believe that in such difficult times, any possible pain relief would be a significant benefit for patients. Furthermore, partaking in this study could be a nice distraction for these patients during these difficult times in the world.]

Below is the questionnaire that will be filled out for every subject:

Buzzy vs Intradermal Lidocaine for Peripheral Intravenous Cannulation in Adults

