 - b. *Where and how data or specimens will be stored:* Data will be stored in a locked cabinet in the PI's office (as described above).
 - c. *How long the data or specimens will be stored:* Data will be stored at least until the results of the study will be published.
 - d. *Specify who will have access to the data or specimens:* The Research team will have access to the data.
 - e. *Specify who is responsible for receipt or transmission of the data or specimens:* The PI will be responsible for the receipt of the data.

- f. **Specify how data and specimens will be transported:** Data will be transported in a closed envelope from the preoperative area and to the PI's office, where it will be stored in a locked cabinet. If data will need to be transferred between research team members for statistical analysis purposes, the word [SECURE] will be included in the subject line of all emails.
- g. **Specify the plan for study data retention and storage (accounting for research team turnover):** Data will remain secure in the PI's office, in a locked cabinet.

I.5 Randomization

Will subjects be randomized?

Yes No

If Yes respond to all of the following:

1. **Describe the randomization procedures, including the ratio of subjects randomized to each study arm:** We will use <http://www.graphpad.com/quickcalcs/index.cfm> to generate a randomized sequence, with a ratio of subjects 1:1 in each arm. <https://www.ncbi.nlm.nih.gov/pmc/articles/PMC3136079/>
2. **Describe the blinding procedures:** The Co-I's that will be conducting the statistical analysis will be blinded to which study arm the subjects were assigned to. N/A the study will not be blinded.

J. Drugs or Devices

1. Will the research involve drugs?

Yes No

If Yes, respond to all of the following:

- a. **If the drug is investigational (has an IND) identify the holder of the IND:** The drug, Lidocaine 2%, is not an investigational drug. It is a commonly used drug that is widely available.
- b. **Describe your plans to store, handle, and administer study drugs so that they will be used only on subjects and be used only by authorized investigators** N/A - this drug is used throughout the hospital for many procedures.
- c. **Who on the research team, in addition to the Principal Investigator, will be accountable for drug(s):** The PI and the Co-Is have access to Lidocaine 2% when they are interacting with patients.

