- f. *Who on the research team, in addition to the Principal Investigator, will be accountable for device(s):* The co-investigators.
- g. *Who will interface with the sponsor:* N/A
- h. *The study device or procedure (including beneficial health care procedures) will be available to subjects after participation in the study:* Yes N/A
- i. *Handouts or instructions sheets that will be given to subjects on how to use study device(s) have been submitted to the IRB:* Yes N/A

K. Study Administration

K.1 Setting

1. *Describe the sites / locations where your research team will conduct the research:* St. Elizabeth's Medical Center
2. *The research will take place at an international site, and the International Guidance and International Checklist were utilized:* Yes N/A

K.2 Registration

1. *Describe the steps the research team will take to ensure that a subject is appropriately enrolled or registered in the study prior to receiving any study intervention (e.g. describe and submit any protocol eligibility checklist that will be used, specify who on the research team will confirm eligibility and that consent was documented, etc.):* Enrollment into the study will be very shortly after the consent process, so the Co-I who will be obtaining consent will not start performing any procedure until he/she obtains the consent.

K.3 Resources Available

1. *Describe the roles/tasks of each research team member here (or alternatively, you may submit any current Delegation of Authority Log you may have which already has this information completed):* The Co-investigators will be enrolling subjects into the study and will be the ones who will be administering the treatment and collecting data. The PI and the Co-I's will be performing the statistical analysis and reviewing each others computations to ensure accuracy.
2. *Describe the qualifications (e.g., training, experience) of the PI and research team to perform their roles. Provide enough information for the IRB to determine the PI and research team are qualified to conduct the proposed research. Alternatively, you can submit the current CVs for the research team instead:* The PI is an anesthesiology attending at St. Elizabeth's Medical Center. The Co-I's are second year anesthesiology resident physicians (aka CA-1's). They have all at least completed medical school training and one year of residency. They are all qualified to obtain consent from patients and have significant experience doing so.

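### I.5 says the analysing Co-Is will be blinded to arm, but F.2 and K.3 take the analysts from the group that treats and enters the data, and no blinding mechanism is described

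*Combined protocol and SAP*

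**What the plan says.** On blinding, I.5 item 2 states: "The Co-I's that will be conducting the statistical analysis will be blinded to which study arm the subjects were assigned to".

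On who does what:

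- **Allocation and treatment (F.2).** After consent, "the Co-I will follow the randomization sheet with which pain-relieving technique to be administered to the patient". Then: "The Co-I will administer the appropriate technique and place the peripheral intravenous catheter".
- **Enrolment and data collection (K.3 item 1).** "The Co-investigators will be enrolling subjects into the study and will be the ones who will be administering the treatment and collecting data". No Co-I is set apart from these tasks.
- **Data entry (F.2).** Once enrolment ends, "the data from the questionnaires will be entered into an excel sheet by one of the Co-I's". A further team member checks the entry.
- **Analysis (F.2).** "one of the Co-I's will perform the statistical analysis and the statistical analysis will be re-checked by a second research team member".
- **Analysis (K.3 item 1).** "The PI and the Co-I's will be performing the statistical analysis and reviewing each others computations to ensure accuracy".

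**The concern.** The comparison is a vibrating ice pack against an injection, so neither patient nor operator can be masked. Blinding of the analysts is therefore the only blinding the plan claims, and a reader of the eventual report would give it weight.

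It would have something to protect. I.2 sends continuous variables to the t-test and categorical ones to chi-square, but does not say which of these the five-level satisfaction item is. No grouping is fixed for catheter size or insertion site, which secondary aims 3 and 4 need. An analyst who knows the arms can see which option favours which technique before choosing. Blinding is meant to prevent that kind of steering. If it is claimed but not carried out, the report is credited with a protection it did not have.

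**Working it through.** No arithmetic applies, since the point does not depend on alpha, power, effect size or sample size. The check is to set the role statements beside the blinding statement and look for anything that reconciles them.

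1. **Does the treating group know the allocation?** Yes. Under F.2 the Co-I takes the technique from the randomization sheet and gives it in person.
2. **Are the analysts outside that group?** No. F.2 has a Co-I analyse. K.3 has the PI and the Co-Is analyse, and describes the Co-investigators as a body as those who enrol, treat and collect data. No independent statistician or non-treating Co-I is named.
3. **Does the I.5 statement cover every analyst?** No. It refers only to Co-Is. K.3 also makes the PI an analyst, and the plan makes no blinding claim for the PI.
4. **Is arm masked in the file?** Nothing says so. F.2 goes straight from questionnaire to spreadsheet to analysis. No A/B code, key-holder or time for opening a key is described.
5. **Is access restricted?** No. I.4 item 5 gives the research team access to the data without distinguishing analysts from the rest.
6. **Do the existing protections hide the arm?** No. The patient seals the completed form so that the treating Co-I does not see the ratings (F.2), and the data carry no subject identifiers (I.4 item 3). The first hides the outcome from the operator and the second hides the name. Neither hides the arm from the analyst.
7. **Would an A/B code be enough without role separation?** Not reliably. With two arms, identifying the technique for one row decodes every row. The target is 30 completers (I.3), and secondary aims 2 to 4 need first-attempt result, catheter size and site in the file. An analyst who treated some of the subjects could plausibly recognise one. This is a reasoned possibility, not something the documents show.

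Steps 1 to 5 leave the I.5 statement with no described means of being true. Step 7 is why the fix needs separated roles as well as coding.

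**The case against.** The strongest reply is that the documents do not rule blinding out. F.2 speaks of one Co-I for entry and, separately, one for analysis, so these may be different people. Each Co-I approaches his or her own patients, so the analyst may have treated few of the 30. A coded file could be prepared without the protocol saying so. All of this stands, and it limits the point to the absence of a described mechanism and to overlap at group level.

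Several stronger readings are tempting but unsupported:

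- **One person randomises, treats, enters and analyses.** The text shows overlap for the Co-I group only. Who generates the sequence is given in I.5 item 1 only as the study team.
- **The words after the blinding sentence, that the study will not be blinded, contradict it.** They may be an unselected template option whose checkbox was lost, so they count neither way.
- **The N/A answer on coding in G.4 item 6 proves that arm is not masked.** That item asks about a key linking study number to name, which is a different matter.
- **The form itself reveals the arm.** The research team's half of the questionnaire is not shown, so this cannot be checked.
- **The missing blinding inflates the type I error by a stated amount.** One could simulate an analyst who picks the smallest of several two-sided P values for satisfaction. Those P values do not change when the arm labels are swapped, so an analyst with a coded file could make the same choice. Such a figure measures open test choice on a secondary endpoint, not unblinding.

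It is also fair to say that this is a pilot meant to establish a baseline and perhaps inform a later sample size. The primary endpoint, a 0 to 10 pain rating, has an evident test in I.2. Both points lower the stakes. Neither makes the I.5 statement accurate.

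**Conclusion.** The concern holds in a limited form. I.5 claims blinded analysis. F.2 and K.3 place the analysis with the group that delivers the allocations, K.3 adds an analyst whom the claim does not cover, and the plan describes nothing that would mask the arm. As described, the stated blinding is not delivered.

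No numerical magnitude is attached. The consequence is a report that would overstate protection against bias in analysis choices, mainly for satisfaction and for the catheter size and site analyses. No effect on the primary result is shown. The conclusion assumes that the readable sections are complete on roles and data handling, and that no separate unpublished procedure supplies the coding. It should be corrected before analysis, but it does not invalidate the trial.

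**What to change.** Amend F.2, I.5 and K.3 so that they agree:

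1. The Co-I who enters the data and the member who re-checks entry record arm only as A or B, hold the key, and take no part in the analysis. The entry checker must be included, because that person may see the arm as well.
2. The analyst and the analysis re-checker receive only the coded file, without any column that reveals the technique.
3. The analyst is the existing team member who treated the fewest subjects, ideally none. If this is the PI, I.5 should extend its statement to the PI.
4. One test per endpoint, including satisfaction, is fixed in writing before the key is opened.

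If the current team cannot do this, delete the I.5 claim and describe the analysis as unblinded.

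The cost is a few sentences and one coded column, with no extra patients. The downside is that those who enter or check the data cannot also analyse. F.2 already calls for two people at entry and two at analysis, so full separation needs 2 + 2 = 4 team members. The documents do not state how many Co-Is there are, so the team must confirm that this is feasible or use the fallback.
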